3.0 Study Specific Aims

3.1 Specific Aims:

1. Perform a double-blind RCT of web-based, portable computerized cognitive training in young individuals with recent onset psychosis receiving treatment within the University of Minnesota, Department of Psychiatry's First Episode Psychosis Program or other state clinics utilizing the NAVIGATE treatment model.
2. Compare the clinical and cognitive effects of neural system-informed TCT that focuses explicitly and specifically on distributed neural system efficiency in auditory/verbal and social cognitive domains, vs. more non-specific GCE designed to enhance executive functioning and problem-solving, vs. TAU. Determine the durability of these effects and their relationship to functional outcome over a 6 month period.

3. As a secondary aim, investigate the feasibility, tolerability, and acceptability of the intervention by service providers, clients, and caregivers in these real-world treatment centers.

3.2 Hypotheses to be tested:

1. TCT participants will show significantly greater gains in general cognition, verbal learning/memory, and social cognition compared to GCE and TAU participants. These gains in the TCT group will be sustained at 6-month follow-up.
2. GCE participants will show improvement in problem-solving and global cognition compared to TAU participants. At 6 month follow-up, GCE participants will show lower gains in global cognition and verbal learning/memory than TCT participants.
3. Gains in general cognition and processing speed, and in social cognition in TCT participants will correlate with improvements on 6-month measures of occupational and social functioning, respectively, as well as internalized stigma. These associations will be significantly greater in TCT participants vs. GCE or TAU participants.
4. Symptom ratings will show improvement in all participant groups at 6 months, with no significant between-group differences.
5. At least 70% of randomized clients will complete >20 hours of training in the TCT and GCE arms.
6. Participants and clinicians will rate the TCT and GCE interventions as equally feasible, tolerable, and acceptable.

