Post-Intervention Assessments (1-4 weeks): After the participants have completed the Intervention Phase, they will be invited to participate in post-intervention assessments. Their appointments will be scheduled after completing the training program, notifying study staff that they no longer wish to participate in training, or after 12 weeks have passed since the Baseline Assessments were completed. The Post-Intervention Assessments should last approximately 5 hours and may be split up into 1-4 visits across 1-4 weeks. We will repeat the baseline measurements in neurocognition, social cognition, clinical symptoms, and functional status, as well as Resource Utilization and Substance Use summary forms. If participants have consented to audio or video recording, their clinical interview will be recorded following the procedures described above.

PROTOCOL TITLE: Minneapolis Community-Based Cognitive Training in Early Psychosis (Mini-COTES)
VERSION 10.0 21 April 2020

In addition to repeating baseline measures, we will measure the feasibility and acceptability of the cognitive training programs through 1) attrition rates; 2) time to completion of training; 3) user and clinician ratings of acceptability.

Participants who completed training will be asked to complete a 22-item, Likert-type questionnaire composed of elements of a measure used previously by Posit Science to evaluate acceptability for their cognitive training software, and components of a measure we have used previously to assess acceptability of training in our recent-onset RCT. Items assess user experience and satisfaction with the programs, the web-based administration, and the training schedule. We will also collect this data from their treating clinician in the First Episode Psychosis clinic. These questionnaires may be completed in-person or collected remotely using REDCap. For participants who are lost to follow up and are unable to provide this data, study staff will complete the Participant Closeout Report to provide some final data on their participation in their case records.

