2: TCT/GCE participants will be encouraged to complete the training in 6 weeks if possible, but will be allowed up to 12 weeks to complete the 30 hours of training. All TAU participants will be followed for 12 weeks.

3: The SCID will only be conducted in complex cases when the MINI will not be sufficient to determine the participant's diagnosis

4: The review of medical records and medication lists will occur within +/-5 days of the scheduled visit.

5: Resource Utilization Survey will be captured at baseline, post-training, and 6-month follow-up. Study staff will use medical records, information from providers, and participant self-report.

6: If the participant disengages from clinical services and is unable to complete the post-training survey, study staff will complete the participant closeout report

7: Participants in the TCT/GCE arm will be asked to complete 5 60 minute sessions of cognitive training per week.

8: During the Intervention phase, the phone check in will be weekly for TCT and GCE participants to update them on training status. Participants randomized to TAU will not be contacted.

9: If there is a period of more than 2 weeks between the 2 appointments at each period (e.g., V1 & V2), the COVID19 Stress Screener will be re-administered at the second appointment.

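### Section 5.2 limits the acceptability survey to participants who completed training, while 6.2, 13.2 and Section 26 imply or permit surveying those who stopped; Hypothesis 6 needs one rule

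*Combined protocol and SAP*

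**What the plan says.** Aim 3 (section 3.1) is to "investigate the feasibility, tolerability, and acceptability of the intervention by service providers, clients, and caregivers". Hypothesis 6 (section 3.2) predicts: "Participants and clinicians will rate the TCT and GCE interventions as equally feasible, tolerable, and acceptable". Section 17.1 tests it with an independent-samples t-test.

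Section 5.2, under Post-Intervention Assessments, names three measures: "1) attrition rates; 2) time to completion of training; 3) user and clinician ratings of acceptability". On the third it says "Participants who completed training will be asked to complete a 22-item, Likert-type questionnaire", and then "We will also collect this data from their treating clinician in the First Episode Psychosis clinic". The same part of 5.2 books post-intervention appointments for several groups, among them people "notifying study staff that they no longer wish to participate in training". Its fallback reads: "For participants who are lost to follow up and are unable to provide this data, study staff will complete the Participant Closeout Report".

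Other places describe the survey differently:

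- Section 6.2 lists the participant survey at post-intervention without a completion requirement. The Closeout Report replaces it only when the participant has disengaged and staff cannot reach them.
- The Section 26 table marks the participant and clinician surveys at the post-training assessment without restriction. Footnote 6 brings in the Closeout Report "If the participant disengages from clinical services and is unable to complete the post-training survey".
- Section 13.2 allows staff to ask people who withdraw from training for post-training data, if they are willing.

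**The concern.** Stopping early is one of the clearest signs that a programme was hard to tolerate. A survey given only to those who finished is therefore conditioned on something close to what it measures. Under 5.2, a participant who quits training but attends the post visit is in the building and is not asked. Sections 6.2 and 26 imply that this person is asked. Staff could follow either rule, and could do so differently from one participant to the next.

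At stake is what Hypothesis 6 means. If people who stopped are left out, similar ratings in the two arms describe those who stayed, not those who were given the programme. Ratings not collected at the time of stopping may not be recoverable later.

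**Working it through.** **1. Who is surveyed under each text.** Take a TCT or GCE participant who stops early, tells staff, and attends the post visit.

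- Section 5.2: not asked, because training was not completed. Not covered by the fallback either, because they are not lost to follow-up.
- Section 6.2 and footnote 6: asked, because they are reachable and the Closeout Report does not apply.
- Section 13.2: may be asked.

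These do not agree. Section 5.2 is the only text that states directly which participants are asked; the others work by implication or permission.

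**2. What counts as completed.** Section 5.2 does not say. It could mean the full 30 hours (4.1, 5.2) or the 20-hour per-protocol minimum (17.1). On the 30-hour reading, even some of the per-protocol set would go unsurveyed.

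**3. Whether anything later restores the ratings.**

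- The intent-to-treat analysis (17.1) cannot use ratings that were never collected.
- Section 17.3 replaces people who discontinue the study and imputes uncompleted tests or items. If no one who stopped is rated, any imputation would have to borrow from those who finished.
- The Closeout Report is completed by staff. Its content is not in the documents, but it is not the participant's own rating.

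**4. Size.** The plan gives no sample size, power or margin for Hypothesis 6, so there is no figure to reproduce. Inputs:

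- c, the fraction completing: 0.70, the lower bound in Hypothesis 5. That bound is for more than 20 hours among all randomized; it is used here as an approximation for those who start.
- g, how much lower those who stopped would rate, in SD of the rating: not in the documents. Assumed 0.3 to 1.0.

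Mean over all starters = completer mean − (1 − c) × g, so completers overstate the arm mean by (1 − c) × g:

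- g = 0.3: 0.30 × 0.3 = 0.09 SD
- g = 0.5: 0.30 × 0.5 = 0.15 SD
- g = 1.0: 0.30 × 1.0 = 0.30 SD

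With the same gap in both arms, the bias in the contrast is g × (difference in completion):

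- equal completion: 0
- 80% versus 60% (assumed), g = 0.3: 0.20 × 0.3 = 0.06 SD
- g = 0.5: 0.20 × 0.5 = 0.10 SD
- g = 1.0: 0.20 × 1.0 = 0.20 SD

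If completion is equal but the gap differs between arms, the bias is (1 − c) × (difference in gaps).

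**The case against.** A reader of 5.2 alone might infer that people who stop are never asked and that Aim 3 is answered only from those who stayed. The documents do not support either statement.

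- Sections 6.2 and 26 make the survey the default for anyone reachable, and 13.2 permits it. The 5.2 wording may have been meant only to separate the trained arms from TAU, who have nothing to rate.
- Aim 3 also uses attrition and time to completion, and Hypothesis 5 counts completion among all randomized clients.
- Section 17.3 compares drop-out and adherence between groups, so one arm losing more people would be seen beside the ratings.
- Hypothesis 6 compares arms, so an equal upward shift in both cancels.
- A contrast of 0.20 SD would seldom change the planned test. With 50 per arm, 0.20 × √(50/2) = 1.0, and two-sided power at 0.05 is about Φ(1.0 − 1.96) = 17%.

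It is also tempting to read 150 of 235 (63.8%) as a training-completion rate. It is not: 235 is the number to be consented across three arms including TAU, and 17.2 counts those who finish both training and the 6-month follow-up.

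All of this stands, and it limits the point. It does not remove it. Time to completion exists only for those who complete. Attrition counts departures without saying how tolerable the training was, and 13.1 lists other routes out, such as worsening clinical status or a lost iPad. Only ratings can answer Hypothesis 6, and the one sentence that says whom to ask leaves out people who stopped. The low power means the t-test may not react; it does not make the estimates unbiased.

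**Conclusion.** Section 5.2 conflicts with 6.2, Section 26 and 13.2 on who rates the training, and leaves completion undefined. If 5.2 is followed, the participant ratings, and by its wording the clinician ratings, come from a selected and probably favourable group. On the assumed gap, the level in an arm is overstated by 0.09 to 0.30 SD at 70% completion. The contrast tested under Hypothesis 6 is affected only if completion or the gap differs by arm. It is not established that people who stopped will go unasked, or that differential drop-out would pass unseen. This concerns a secondary aim, but is worth settling while participants who stop can still be asked.

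A separate and minor matter: Aim 3 names caregivers, and the background (2.2) speaks of their ongoing feedback, but neither 6.2 nor Section 26 lists a caregiver instrument. One might conclude that the caregiver part cannot be answered at all. That goes too far, since feedback is foreseen; what is missing is a stated way to collect it.

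**What to change.** - In 5.2, and consistently in 6.2 and Section 26, make the survey population *all participants randomized to TCT or GCE who started training*, together with their treating clinicians.
- Give the survey when a participant says they are stopping, or at the post visit, using the REDCap route that 5.2 already provides. Keep the Closeout Report for those who cannot be reached.
- Define completed training in hours.
- In 17.1, test Hypothesis 6 on all starters who respond, report the response rate by arm, and show completers separately.
- Reconcile the mention of caregivers in Aim 3 with the instrument list, by adding an instrument or removing the word. The family member or friend nominated under 20.1 is someone with whom staff may discuss the participant; that permission does not by itself allow research data to be collected from them.

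The cost of the main change is small: a wording change and an existing survey sent to more people. Some who stopped will not reply, so selection is reduced and not removed, and mean ratings may be less favourable. A caregiver survey would cost more, because it would need its own permission.

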6.0 Data Banking

6.1 Storage and Access:

All data management servers will meet all relevant privacy and security standards for electronic clinical trial data entry and storage, as well as HIPAA standards for confidentiality and privacy.

Access to study data, particularly data with identifying information, will be limited to individuals listed on the delegation of authority log, or those who have the authority to review study records. Identifying information will not be shared outside of the UMN study team and its collaborators (the University of California San Francisco, Posit Science Corporation, and the University of Pennsylvania) unless required by law. Study staff will only be provided with access to the study data that they need to perform their work duties.

All identifying information will be maintained for a minimum of six years after the completion of the study in compliance with HIPAA regulations. Any data use agreements that allow for the sharing of study data will be maintained for a minimum of two years past their expiration.

For a visual representation of the flow of study data, please refer to Appendix 1.

Consent documents:

PROTOCOL TITLE: Minneapolis Community-Based Cognitive Training in Early

Psychosis (Mini-COTES)

VERSION 10.0 21 April 2020

Consent documents, including UBACC, HIPAA Authorizations, and communication authorizations, will be collected and stored in UMN REDCap. If need be, participants may still complete paper consent documents. Copies of physical consents will be uploaded into a dedicated folder within Box, while the originals will remain in locked cabinets in locked offices. The consents will be separated from the participant binders to keep participant PHI separated from study data. Locations of the consent forms will be documented within the regulatory files and OnCore system. These records will only be made available to study staff and will not be shared with any collaborators. Consent documents will not be shared outside of the UMN study team unless required by law.

If a participant has requested to receive a copy of their signed consent forms over email, study staff may temporarily download the consent documents from REDCap or Box to their AHC-IS computer in order to attach the file to an email.

Assessment and Training data:

The majority of the assessment data will be collected on paper forms, which will be kept in individual binders for each participant. These binders will be stored in locked cabinets in locked offices. Certain self-report assessments may be collected and stored in UMN REDCap.

For visits conducted remotely or if binders are inaccessible, study staff may temporarily download digital versions of these assessment forms to their ACH-IS computer in order to take notes. Once complete, staff will upload the digital files to the participant's folder on Box. Scores may later be recorded in a participant's binder to facilitate first and second scoring. Additionally, several assessments include participant-facing documents that are normally handed to participants during in-person appointments. Study staff will email participants a PDF copy of these documents for their reference during remote visits.

Some activities will involve computerized programs. All assessments or scoring of assessment data will involve AHC-IS managed computers. The study team will loan AHC-IS managed iPads to some participants in order to complete their BrainHQ cognitive training at home. Study staff will wipe the iPad when it is returned to the lab to remove any previous data (i.e., Wifi log in information) that may have been stored on the device.

Several assessments will involve MCCB software that is installed on lab computers. The CPT-IP assessment will be conducted on an assessment laptop. The results will be printed off and stored in the participant's binder. The MSCEIT 4 software (part of the MCCB software package) will be used to

PROTOCOL TITLE: Minneapolis Community-Based Cognitive Training in Early Psychosis (Mini-COTES)
VERSION 10.0 21 April 2020

grade the MSCEIT assessment. The MCCB T-scores will be generated with the MCCB scoring program. An Excel Spreadsheet will be used to calculate the standardized scores for the Faux Pas and Social Functioning Scale assessments; these data will not contain PHI and will not be saved. Study staff will take outcome scores from the participant's binder and enter it into the programs to obtain standardized scores, which will be recorded on the participant's summary score sheet in their binder. The outcome scores for the CPT-IP, MCCB, and the MSCEIT will be saved to the computer but will not contain any PHI; all data is stored underneath the participant's ID and visit code. Study team members will regularly delete the data from the computers after the data has been entered into the participant's binder and the REDCap database.

Performance data for the Penn CNB will be collected through the University of Pennsylvania Penn CNB portal and will be stored on University of Pennsylvania secure servers. The data collected will not contain any direct identifiers; instead, the data will be associated with the participant's unique study ID. However, study staff will enter the participant's date of birth into the web portal to confirm the participant's age at time of assessment. Participants are given a coded identifier at the beginning of a testing session by a researcher and no other identifiable information is required to begin a testing session and collect data on the Penn CNB. The data will be exported from University of Pennsylvania servers to Box at interim and final analyses and merged with the master data set. This data will remain on University of Pennsylvania servers and on Box indefinitely.

Performance data from BrainHQ cognitive assessments will be collected on the BrainHQ web portal. Data collected during remote cognitive training will be collected through the BrainHQ iOS app. All BrainHQ data will be stored on secure servers hosted by Posit Science Corporation; no data will be stored locally on devices running the BrainHQ software. Study staff will create an account for the participant to complete their training and their cognitive assessments. Direct identifiers will not be shared with Posit Science. A BAA exists between Posit Science and the University of Minnesota Department of Psychiatry to allow sharing of participant data. Posit Science will maintain records of all data generated in this study to use for their own purposes indefinitely. Study staff will extract the assessment data from the BrainHQ website and store this data in Box for further analysis. Please refer to section 18.0 Confidentiality for information about the de-identification of data.

Data from this study will be entered into the University of Minnesota Mini-COTES REDCap database. As this study is being conducted in partnership with the COTES protocol at UCSF (see study "Community-Based Cognitive Training in Early Schizophrenia," 1607S90201), this database will later be

PROTOCOL TITLE: Minneapolis Community-Based Cognitive Training in Early Psychosis (Mini-COTES)
VERSION 10.0 21 April 2020

merged with the University of California San Francisco COTES REDCap database for permanent storage. At the end of the study, the UCSF REDCap data will be extracted to UMN Box for further analysis. This data will contain some PHI in the form of date of birth and date of data collection, but will not contain participant names or contact information. The study team has a DUA with UCSF to allow for the sharing of this data between institutions.

Video or Audio Data:

Video/audio data will be recorded with a camcorder using an SD card. After the assessment appointment is complete, a member of the study staff will upload the file into a secure folder within Box. If the study staff is not able to immediately upload the video/audio file onto Box, the device will be stored in a locked cabinet in a locked office until the upload can be completed. Once the study staff has confirmed that the file has successfully uploaded to Box the video/audio file will be erased from the device. In the case that a video/audio file needs to be downloaded off of Box for viewing it will be stored on an AHC-IS supported computer. The audio/video data will be deleted from the computer after viewing is complete. However, this option will only be used if absolutely necessary; whenever possible, all viewing will take place within the Box server. Access to the folders will be shared with qualified study staff and collaborators on a per-need basis, and only qualified study staff listed on the delegation of authority log will have access beyond Viewer level. Study staff will regularly check who has permissions to the video/audio folder and will remove users who no longer need access to the files. Video/audio data will be stored indefinitely if the participants agreed to have their video/audio data used for other research purposes or for training purposes. If participants did not consent to these uses of their video/audio data, the files will be erased when data analysis for this project is complete.

Other Study Data:

Participants will be asked during their consent form whether they would like to be contacted in the future for additional opportunities to participate in research. Should they agree to do so, their name, contact information, and relevant demographic information such as age, gender, and/or diagnosis will be added to a potential participant registry. This information will be maintained in Box by the study team, and may be disclosed to collaborators with IRB-approved studies. This information will be disclosed to participants in the consent form.

PROTOCOL TITLE: Minneapolis Community-Based Cognitive Training in Early

Psychosis (Mini-COTES)

VERSION 10.0 21 April 2020

An enrollment log containing the participants' personally identifying information, including name and contact information, will be stored in Box in a dedicated study folder. Only qualified UMN study staff will have access to the study folder. This enrollment log will also maintain the key between study ID numbers and personal identifiers, including alternate IDs (e.g., Posit Science). These records will be maintained for a minimum of six years after completion of the study.

If a participant has consented to text messaging, text messages sent to and from participants will temporarily be stored on a University cell phone. The cell phone will not store the participant's name in the contact list of the device; study staff may store the participant's number under their study ID code in order to recognize them during text conversations. When the participant has completed the study or withdraws, their contact information will be deleted from the phone. When the cell phone is not in use, it will be stored securely (e.g., in a locked cabinet in a locked office). Primarily the phone will be stored at the Department of Psychiatry. However, staff may take the phone with them during certain circumstances, such as: travelling between research sites; in preparation for weekend appointments; and when working from home. The phone will be locked with a passcode and will not have pop-up messages enabled on the locked screen; study staff will need to unlock the phone and navigate to the messages to read the contents of any texts received by participants. Text messages will be regularly deleted from the cell phone (at least weekly) to protect participant PHI. If the text messages are of significant concern (e.g., indicate a safety issue), the contents of the messages will be saved for future review using screenshots of the conversation.

Emails that participants send to study staff will not be deleted and will be maintained as part of the study record, until documents containing PHI for the study are deleted. If the emails include significant information relevant to the participant's health or study status, they will be maintained indefinitely as part of the study record. Access to the study email account will be limited to members of the study team who coordinate appointments with study staff, though access can be provided as required for institutional review.

In order to be reimbursed for parking, participants must email or text a picture of the parking receipt to staff, or bring the receipt to staff at their next appointment. For audit purposes, staff will save these pictures to a dedicated folder on Box.

If a potential participant does not qualify for the study based on the phone screen, study staff will ask if they would like to be contacted for other research opportunities in the future. If the individual agrees, the study staff will gain verbal permission to store their phone screen and add their

PROTOCOL TITLE: Minneapolis Community-Based Cognitive Training in Early Psychosis (Mini-COTES)
VERSION 10.0 21 April 2020

contact information to a research registry. The phone screens will be stored in a locked drawer in a locked office and scanned into Box.

6.2 Data: Copies of all assessments used in the protocol (including obsolete versions) will be included in the Regulatory Binder. For online assessments (e.g., the Posit Science Auditory Sweeps), directions to access the portal will be included. For measures sensitive to practice effects (e.g., HVLT, BVMT), we will use alternate forms. Practice effects between-groups are controlled for by the study design. A counterbalancing sheet has been established to ensure participants receive alternate versions of the forms in proper order.

For a complete Schedule of Events, please refer to Section 26.

Assessments that can be completed remotely have been indicated with an asterisk*.

Neurocognitive Assessments:

- MATRICS Consensus Cognitive Battery [MCCB, (59)]
 - Trail Making Test: Part A
 - Category Fluency (Animals Only)*
 - Brief Assessment of Cognition in Schizophrenia (BACS) Symbol Coding
 - Continuous Performance Test—Identical Pairs (CPT-IP)
 - Wechsler Memory Span (WMS) Spatial Span
 - UMD Letter-Number Span*
 - Hopkins Verbal Learning Test (HVLT) Learning Trials: Immediate and Delayed Recall*
 - Brief Visuospatial Memory Test (BVMT) Immediate and Delayed Recall
 - Neuropsychological Assessment Battery (NAB) Mazes
 - Mayer-Salovey-Caruso Emotional Intelligence Test (MSCEIT)*
- Wechsler Test of Adult Reading (WTAR) (Baseline only)*
- Penn Emotion Recognition Test (61)*
- Penn Facial Recognition Test: Delayed Recall*
- Penn Prosody Identification [PROID, (62)]*
- Posit Science Auditory Sweeps Test*

Clinical and Functional Assessments

- Demographics*
- Substance Use Summary*
- Medical History review*

PROTOCOL TITLE: Minneapolis Community-Based Cognitive Training in Early Psychosis (Mini-COTES)
VERSION 10.0 21 April 2020

- Mini International Neuropsychiatric Interview (MINI) (Baseline only. Suicidality module not used to determine suicidality risk; C-SSRS will be used instead)*
- Structured Clinical Interview for DSM 5 (SCID) (Baseline only; only in cases where the MINI is not sufficient to deliver a clinical diagnosis)*
- Positive and Negative Syndrome Scale [PANSS, (63)]*
- The Quality of Life Scale—Abbreviated [QLS, (65)]*
- UCSD Performance Based Skills Assessment [UPSA-Brief, (49)]
- Social Functioning Scale [SFS, (66)]*
- Internalized Stigma of Mental Illness Self Report [ISMI, (67)]*
- Global Functioning Role and Social*
- Global Assessment of Functioning (GAF-M)*
- Clinical Assessment Interview for Negative Systems (CAINS) Self Report*
- Behavioral Inhibition System/Behavioral Activation System (BIS/BAS) Scales*
- Temporal Experience of Pleasure Scale [TEPS, (71)]*
- Columbia Suicide Severity Rating Scale (C-SSRS)*
- Faux Pas*
- COVID19 Stress Screener*

Feasibility and Acceptability

- Post-Training Participant Survey (Post-Intervention only)*
- Participant Closeout Report (Post-Intervention only; only if the participant disengages from services and the study staff is unable to contact them to complete the post-training survey)*
- Post-Training Clinician Survey (Post-Intervention only)*
- Computer Utilization survey*

6.3 Release/Sharing:

Participants will be asked in their consent form whether they consent to the research team using their data for future research projects; this answer will be referenced before including the participant in other data sets.

BrainHQ assessment and training data will be collected and maintained by Posit Science to perform analyses and for the preparation of manuscripts, presentations, and other dissemination of results to the public. Additionally, Posit Science may use the data collected in this study for project development and quality assurance purposes. Posit Science may share the de-identified data sets with collaborators as they see fit. Please refer to Section 18.0 Confidentiality for information about the de-identification of study data.

PROTOCOL TITLE: Minneapolis Community-Based Cognitive Training in Early Psychosis (Mini-COTES)
VERSION 10.0 21 April 2020

Penn CNB assessment data will be collected and maintained by the University of Pennsylvania and may be used to perform analyses and to prepare manuscripts, presentations, and other dissemination of results to the public. Additionally, the University of Pennsylvania may use the data collected in this study for project development and quality assurance purposes. The University of Pennsylvania may share the data sets with collaborators as they see fit.

Assessment data may also be shared with other collaborators outside of the UMN, with the permission of the PI. If the collaborator is interested in using the BrainHQ data or Penn CNB data, permission from Posit Science or University of Pennsylvania must also be obtained. Outside collaborators will be required to enter into a Data Use Agreement with the PI, Posit Science, and the University of Pennsylvania, as applicable. Most likely a limited data set will be shared (e.g., date of collection will still be included), but the data set may be completely de-identified if required by the agreements. Data shared with any collaborator (UMN or outside) will never contain direct identifiers. Study staff will verify that the data set has no direct identifiers by having two staff members review the data set to ensure that all necessary information has been removed. The exact methods of access and the data shared will be detailed in the data use agreements. These records will be maintained for a minimum of two years after the expiration of the agreement.

De-identified study data will be shared with our collaborators at University of California San Francisco. Study staff will upload data to a shared database in UCSF's REDCap server. This data will not contain participant identifiers, but will contain appointment dates. Staff at UCSF may use this data in analyses with the COTES study data (see study 1607S90201). If participants have authorized their data to be used in future studies, the UCSF team may also use this data for additional analyses.

Video/audio data will only be shared with outside collaborators if the participant has authorized for their recordings to be used for other research projects. Collaborators will need to have the permission of the investigators and an appropriate data use agreement in place to ensure the protection of participant identities. Appropriate restrictions for use of the data will be included in the terms of the data use agreement. As much as possible, collaborators will only be given Viewer access to the files and will not be able to download the video/audio file to an external device. Study staff will regularly check who has permissions to view the video/audio files and will remove access for any individuals who no longer need to view the files.

Some participants may authorize that the study team can use their video or audio recordings in scholarly presentations or publications. In these instances, the study team will attempt to limit the ability to identify the participant while still providing

PROTOCOL TITLE: Minneapolis Community-Based Cognitive Training in Early Psychosis (Mini-COTES)
VERSION 10.0 21 April 2020

meaningful data to the intended viewers. Examples of methods used may include blurring the participant's face or using only the audio for video clips.

Additionally, study participants may authorize that their audio or video files can be used for training research staff in the future. In this case, trainee staff can view their clinical assessments to learn how to conduct interviews and to compare assessment scores against the original assessor.

Some assessment measures are used in other studies in the Department of Psychiatry (e.g., the MINI 7). In order to reduce the time and effort involved in repeating these measures, participants will have the option to allow the study team to share the information from these measures and computerized tests with other study teams. If they agree, staff will ask if they are participating in any other research studies in the Department of Psychiatry. Staff will reach out to that study team to see if they could share study information. Similarly, if the participant joins another study after enrolling in this one, the study team could share information from the same study activities with that study team. If the participant is also enrolled in the COPRR study, data may be shared with this database and with other research teams through this platform. This option to share data will be included in the optional elements of the consent form.

